### 4.3 Duration of subject participation

A subject may be involved in the study for approximately 17.5 months from screening to the final follow-up visit. "End of study" is defined as the time point when the last subject has completed the last study visit.

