#### 8.9.3 Recording instructions

Each subject with an AE occurring after randomization and through study exit should be fully recorded in the source document for further transcription to the eCRF. Each subject should be questioned about AEs at each study visit following randomization. The question asked should be, "Since your last clinical visit have you had any health problems?" Information on AEs can also be obtained from signs and symptoms detected during each examination.

When an AE is related to a device deficiency including technical device malfunction, the AE should be recorded in the AE eCRF and technical complaint should be reported separately on the study complaint form.

Investigators, or other study site personnel, should record all AEs in the eCRF, including:

- a) Event term (recorded in standard medical terminology and avoiding abbreviations)
- b) Description of event and affected area
- c) Start date (first day with symptoms)
- d) Stop date (last day with symptoms)
- e) Intensity (mild, moderate, or severe according to definition in Section 8.9.3.1)
- Seriousness (serious or not serious, according to definition in Section 8.9.3.2)
- g) Causal relationship to study product or study product injection procedure (yes or no)
- h) Action taken (none, medication treatment, non-medication treatment, or other procedures/tests, subject withdrawn)
- Outcome of the AE (ongoing, recovered, recovered with sequelae, death, chronic/ stable, not recovered at the end of the study)

The pre-defined, expected post-treatment events should be assessed separately. These events should be collected by subjects in a diary used daily for 28 days after the treatment.

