# 8.9.7 Follow-up of ongoing related events after termination of the study and events with onset after termination of study (subject last visit)

All serious as well as non-serious AEs with a causal relationship to the study product or treatment procedure and ongoing at study end, should be followed up after the subject's participation in the study is over. Such events should be followed-up after the last study visit until resolved, or assessed as chronic or stable. All AEs assessed as related to the

2021-02-09 21:57

study product or treatment procedure, serious as well as non-serious, with onset after the study termination (last subject study visit), and that the Investigator becomes aware of, should be reported to the Sponsor by email to

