13.1 Adverse Events

Adverse events (AEs) will be summarized for the safety population. All AEs will be coded using MedDRA and presented by MedDRA system organ class (SOC), preferred term (PT), and treatment.

Only AEs occurring after first injection for subjects randomized to Treatment or after randomization for subjects randomized to No Treatment will be included in analysis. AEs occurring before, if any, will only be listed in subject data listings.

All AE endpoints will be summarized by treatment as follows:

- i) No treatment at baseline, includes subjects randomized to No Treatment up until the time of their first injection.
- ii) Initial treatment with Restylane Defyne, includes subjects randomized to Defyne (after their first treatment up until their

🖧 GALDERMA	43USCH1702 Statistical Analysis Plan

Title

iii)

optional retreatment) pooled with the controls (i.e., subjects randomized to No Treatment) after their optional initial treatment. Retreatment with Restylane Defyne, includes subjects randomized

to Defyne after their optional retreatment.

A summary of AEs will be provided, which will include:

- i) number of subjects with at least one AE and number of events (in total as well as serious AEs)
- ii) number of subjects with at least one AE, related to study product or injection procedure, and number of events (in total as well as serious AEs)
- iii) number of subjects with at least one AE, unrelated to both study product and injection procedure, and number of events (in total as well as serious AEs)
- iv) number of subjects who did not have an AE

AEs will be summarized by SOC, PT, and severity.

The number of subjects with AEs related to study product or injection procedure as well as the number of events will be summarized by SOC, PT, and severity. Untreated subjects in control group cannot have a related AE and hence cannot be included in this table.

In addition, for related AEs, the number of days to onset and the duration of event will be summarized by SOC and PT using mean, SD, min, max and median.

Time to onset of an AE will be derived as the start date minus the date of most recent treatment. If the start date is missing, it will be assumed that the AE started on the day of most recent treatment.

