Duration of an AE will be derived as the stop date minus the start date + 1. If the start date is missing, it will be assumed that the AE started on the day of most recent treatment. Missing stop date will not be imputed and therefore no duration will be calculated in these cases. Instead, the number of AEs that were ongoing at the end of the study will be given.

If a subject has more than 1 AE of the same PT and there are different grades of severity, only the highest grade will be represented in the summary of severity. If the severity assessment is missing, the highest level of severity will be assumed.

•• G	ALDERMA	43USCH1702 Statistical Analysis Plan	Doc id
		Each AE will be assessed for relatedness to the study product injection procedure. The Investigators will be asked to indicat to each of the following questions in the eCRF: "Do you consider that there is a reasonable possibility	t and for the e a response

Action taken for related AEs will also be summarized.

To evaluate consistency of the results across different subgroups, AEs will also be analyzed across different subgroups as described in the exploratory objectives (see Section 3.1.4).

All reported AEs will be listed in data listings including time to onset, duration of AE and timing of the AE. Timing would be the variable indicating whether the AE occurred after no treatment, initial treatment, or optional retreatment.

By-subject listings also will be provided for all subjects (safety population) for the following: AEs related to study product or injection procedure, AEs resulting in discontinuation of study product, and serious AEs.

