15.0 TABLES AND LISTING CONVENTIONS

Mock-ups for statistical tables and listings will be provided. Final formats for the statistical tables and listings may deviate from these mock-ups upon agreement with Galderma. Footnotes will be used as needed to clarify the information that is presented in the tables and listings. Unless otherwise requested by Galderma, the term 'subject' will be used in all tables and listings, in accordance with Clinical Data Interchange Standards Consortium (CDISC) standards.

The general layout of tables and listings will be as follows:

43USCH1702 Statistical Analysis Plan

All tables and listings will use landscape orientation. Margins will be at least 2.0 cm at the top and bottom and at least 0.8 cm on the left and right, excluding headers and footers, in accordance with electronic Common Technical Documents (eCTD) guidelines. Font will be Courier New, unless otherwise specified, with a 10-point font size in most cases. Page numbering will be sequential within each table, listing, and figure. Column headers should be in initial capital letters. Units for numeric data will be included when appropriate.

Tables and data listings will be created from different SAS programs. A single program may produce multiple tables or multiple data listings from the same dataset (e.g., all clinical chemistry data listings may be generated by a single program).

Mock-ups for statistical tables will include headers, title numbers, titles, column headers and footers, and a proposed layout for the display of data. The final decision on the precision (i.e., number of decimal places) for presentation of descriptive statistics will be made by Galderma after review of draft statistical tables and before database freeze.

Mock-ups for data listings will include headers, title numbers, titles, column headers, and footers. Data listings will provide all data either collected on the corresponding eCRF page or loaded directly into the database, unless otherwise indicated. If there are too many fields to be fit into a single page, data should be grouped logically and the listings will be generated as Part I, Part II, etc.

In general, data listings should include all subjects with data. However, if only subjects who meet a certain condition are listed (e.g., subjects with SAEs) and no subjects meet the condition, the data listing will so indicate.

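### Minor: duration statistics for related AEs cover only events with a stop date, and the count given for ongoing events does not show how long they have lasted

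*SAP*

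**What the plan says.** For related AEs, SAP 13.1 states that "the duration of event will be summarized by SOC and PT using mean, SD, min, max and median". Protocol 10.5 plans the same statistics. SAP 13.1 defines duration as stop date minus start date plus one day. It then sets the rule for open events: "Missing stop date will not be imputed and therefore no duration will be calculated in these cases". The substitute follows at once: "Instead, the number of AEs that were ongoing at the end of the study will be given". The visible text plans no censored-data method and no summary of elapsed time for open events.

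Four other places bear on this:

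- **Protocol 8.9.3** defines the stop date as the final day with symptoms. Its outcome categories keep ongoing, chronic/stable and unrecovered at study end apart from the recovered categories and death.
- **Protocol 8.9.7** requires follow-up of related events still open at study end: "Such events should be followed-up after the last study visit until resolved, or assessed as chronic or stable".
- **SAP 13.1** keeps every event visible individually: "All reported AEs will be listed in data listings including time to onset, duration of AE and timing of the AE". It also plans a separate by-subject listing of related AEs.
- **SAP 15.0** provides calendar dates and study days in the listings where applicable, and says of the displays: "Footnotes will be used as needed to clarify the information that is presented in the tables and listings".

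**The concern.** Whether an event has a stop date is not independent of how long it lasts. An event is still open at last contact mainly because it is long or because it started late. Leaving such events out of the statistics removes the long end of the distribution, so the mean and maximum lean short, and the median does so to a smaller degree.

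The maximum matters most, because readers use it to judge how long a related event can last. It can be below a duration already observed in an open event, and a count cannot reveal that. SAP 13.1 tabulates AEs by treatment period. The period after optional retreatment starts later for a given subject, so less follow-up remains and its durations are cut off sooner.

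The stake is how a descriptive safety table is read. No test depends on it.

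**Working it through.** The plan states no figure on this point, so there is nothing to reproduce. The check is a reading of the text followed by an illustration on assumed inputs.

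**Step 1. Which events get a duration.** Duration needs both dates, and a missing stop date is not imputed. The statistics therefore describe events with a stop date only. The remaining events are represented by the number ongoing at study end. That number need not equal the number without a stop date: an event may have ended on an unknown date, and the visible text does not say how a chronic/stable event is counted.

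**Step 2. A hypothetical term with 10 related events.** Eight close after 7 days and two are open at 300 days. The table shows mean 7, maximum 7 and two ongoing. Using the time already observed for the open events, the mean is at least (8 × 7 + 2 × 300)/10 = 65.6 days and the longest is at least 300.

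**Step 3. How far the statistics could move.** All inputs are assumed except one upper limit for follow-up. Protocol 4.3 says "A subject may be involved in the study for approximately 17.5 months from screening to the final follow-up visit", and 17.5 × 30.4 = 532 days. This is an upper limit because it runs from screening.

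- Durations are exponential with mean 7 days (short) or 180 days (long), mixed 100/0, 95/5 or 80/20. The one-day convention is ignored.
- Follow-up after onset is either fixed at C (case A) or uniform on 0 to C (case B), with C = 365 or 532 days.
- No credit is given for stop dates obtained under Protocol 8.9.7.

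With weights w, means m, density f and survival function S(t) = Σ w·exp(−t/m):

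- Case A reported mean = Σ w[m − (C + m)·exp(−C/m)] / (1 − S(C)).
- Case B: closed durations have density proportional to f(t)(1 − t/C) on 0 to C, integrated numerically.

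Worked example (80/20, C = 365, case A): exp(−365/180) = 0.1316, so S(C) = 0.2 × 0.1316 = 0.0263. The numerator is 0.8 × 7 + 0.2 × (180 − 545 × 0.1316) = 5.60 + 21.65 = 27.25. The reported mean is 27.25/0.9737 = 27.99 days, against a true mean of 0.8 × 7 + 0.2 × 180 = 41.6.

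| Mixture | True mean / median | C | A: mean / median / open | B: mean / median / open |
|---|---|---|---|---|
| 100/0 | 7.0 / 4.9 | 365 | 7.0 / 4.9 / 0% | 6.9 / 4.8 / 1.9% |
| 100/0 | 7.0 / 4.9 | 532 | 7.0 / 4.9 / 0% | 6.9 / 4.8 / 1.3% |
| 95/5 | 15.7 / 5.2 | 365 | 12.1 / 5.2 / 0.7% | 9.2 / 5.0 / 4.0% |
| 95/5 | 15.7 / 5.2 | 532 | 13.8 / 5.2 / 0.3% | 10.5 / 5.0 / 2.9% |
| 80/20 | 41.6 / 6.7 | 365 | 28.0 / 6.4 / 2.6% | 17.0 / 5.7 / 10.1% |
| 80/20 | 41.6 / 6.7 | 532 | 34.5 / 6.6 / 1.0% | 21.9 / 6.0 / 7.5% |

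**Step 4. The maximum.** In case A every open event has already lasted C days, longer than any closed one. The chance that the tabulated maximum is below an observed duration is then 1 − (1 − S(C))^n for n events in a term. For 80/20, C = 365 and n = 10 this is 1 − 0.9737^10 = 0.234. Case B was simulated with 400,000 datasets per setting.

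| Mixture, events per term | A: C = 365 / 532 | B: C = 365 / 532 |
|---|---|---|
| 80/20, n = 10 | 23% / 10% | 42% / about 31% |
| 80/20, n = 3 | 8% / 3% | about 22% / 16% |
| 100/0, n = 3 or 10 | 0% / 0% | 2% / 1% |

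**The case against.** The strongest reply is that this is a stated convention and not an omission. The SAP says what it will do and supplies a count, and a non-zero count already warns the reader that the statistics cover closed events only. With about 140 subjects, the related-AE listing should be short and its dates allow elapsed time to be worked out. Protocol 8.9.7 requires follow-up of just these events. The table shells are not in the public copy, so the label and number of events may already be there.

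Much of this stands. It fixes the grade as minor and removes any suggestion of concealment. It does not remove the point, because a count still does not tell the reader that the tabulated maximum is below something already observed.

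A reader might infer three stronger things that the documents do not support:

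- **That an event closed as chronic or stable necessarily has no stop date, and so no duration.** The stop-date definition and the end of follow-up make this plausible, but it depends on eCRF completion rules that are not visible.
- **That the planned duration figures are materially wrong.** The illustration rests on assumed durations and mixtures, and its largest values need one long event in five together with short follow-up for many events.
- **That every event without a stop date should be treated as lasting to last contact.** An event that recovered on an unknown date would then be overstated and could become the displayed longest duration. A stop date missing for such a reason has no fixed direction of effect.

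**Conclusion.** The point holds as a minor, inexpensive improvement. The duration statistics for related AEs describe events with a stop date, and ongoing events are given a count without a length of time. If related events are unresolved, the mean and maximum lean short.

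The size cannot be found from the documents. It is nil or negligible if related events are short or all resolve. In the assumed 80/20 mixture the reported mean is 17 to 35 days against 41.6, while the median moves by at most one day. Stop dates obtained under Protocol 8.9.7 would reduce the effect, but the visible SAP text does not say whether they enter the table. Nothing here touches a hypothesis test or the primary analysis.

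**What to change.** Keep the planned statistics and revise the duration paragraph of SAP 13.1 along these lines:

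> Duration statistics are for related AEs with a stop date and will be labelled so. Any stop date in the locked database will be used, including one obtained under Protocol 8.9.7. Beside these statistics, by SOC, PT and treatment period, the table will show the number of related AEs that have no stop date and whose recorded outcome is unresolved (ongoing, chronic/stable, or unrecovered at study end), with their longest observed duration. Observed duration is the date of last study contact minus start date + 1. Related AEs that recovered, or otherwise ended, on an unknown date will be counted separately and given no observed duration.

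The existing rule for a missing start date can stay. If a Kaplan-Meier median is added as an option, only the unresolved events should be censored at last contact. That median may not be reached where many events are open.

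The cost is one SAP paragraph, light programming on dates already collected, and a wider table.

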13.2 Pre-defined, expected, post-treatment events

The local tolerability is evaluated by subject in a 28-day diary for the chin, starting on the day of treatment. The presence of pre-defined expected post-treatment events, i.e. bruising, redness, swelling, pain, tenderness, lumps/bumps, itching, and other are assessed for the treated area.

Diary data will be counted and displayed separately from other AE data.

Number and percentage of subjects reporting each pre-defined, expected, post-treatment symptoms, as collected in the 28-day diary, will be presented in total and by maximum severity. Number of days with the event will be presented by treatment group and category: 1-3, 4-7, 8-14, and 15-28.

The local tolerability data will be presented by treatment and subject in data listing.

13.3

13.7 Laboratory Assessments

For all women of childbearing potential, a urine pregnancy test will be performed at screening and all injection visits prior to treatment.

The pregnancy test data will be presented by treatment and subject in data listing.

13.8 Concomitant Medications and Concomitant Procedures/ Treatments

The number and percentage of subjects reporting concomitant medications will be summarized by treatment. In addition, the number and percent of subjects reporting concomitant medication, and the number of drugs (total number and the number of ongoing drugs), will be summarized by reason. The same summary will be done for concomitant procedures/treatments. Also, the number and percentage of the subjects who took each medication will be tabulated by WHO Drug Dictionary Anatomical Therapeutic Chemical 4thlevel (ATC-4) and preferred name for concomitant medications. If the 4th level term is not available, the next available level (e.g., ATC-3) will be used. A subject will only be counted once within each ATC-4 code and within each preferred name. Concomitant medications that started due to an AE will be summarized separately.

All concomitant medication and concomitant procedures/treatments data will be presented by treatment and subject in a data listing.

14.0 QUALITY CONTROL

All data displays and analyses will adhere to the International Conference on Harmonisation (ICH) Harmonized Tripartite Guideline: Structure and Content of Clinical Study Reports (ICH Topic E3).

All analyses will be performed using SAS® Version 9.4 (or later). Advanced Clinical will follow its standard operating procedures in the creation and quality control of all tables, listings, figures, and analyses. Galderma or its designee will review all tables, listings, and figures prior to final database lock. All final SAS programs and associated output files will be transferred to Galderma in agreed-upon format at project completion.

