## 9. Data Handling and Management

#### 9.1 Data management

Data management based on GCP refers to the activities defined to achieve safe routines to enter clinical data information into a database, efficiently and avoiding errors. The data management routine includes procedures for handling eCRFs, database set-up and management, data entry and verification, data validation, and documentation of the performed activities including information of discrepancies in the process. The data management process will be described in detail in the data management plan (DMP).

The database, the data entry screens and program will be designed in accordance with the CIP and the eCRF. Data validation will be performed by computerized logical checks and manual review. Drugs and events will be coded in accordance with World Health Organization (WHO) Drug and medical dictionary for regulatory activities (MedDRA) dictionaries as specified in the DMP. SAEs in the clinical database will be reconciled against the data in the safety database.

When all efforts have been made to ensure that the data recorded in the eCRFs and entered in the database is as correct and complete as possible, the clinical database will be locked. Study data will be transferred to SAS datasets which thereafter will be write-protected. Statistical analyses will be generated in SAS using data from the locked datasets.

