5.2 Per-Protocol (PP) Population

Includes all subjects in ITT who complete the Week 12 visit without any deviations considered to have substantial impact on the primary effectiveness outcome.

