5.3 Safety Population

Includes all subjects who were treated with *Restylane® Defyne* or randomized to no treatment control group. Subjects are analyzed based on the as treated principle (i.e. according to the treatment actually received).

The primary and secondary effectiveness analyses will be performed using the ITT analysis set. The primary and the first secondary effectiveness analysis will be repeated using the PP analysis set if there is at least a 10% difference in the number of subjects between the PP and ITT sets. The safety evaluations will be performed based on the safety analysis set.

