7.0 PROTOCOL DEVIATIONS

Protocol deviations will be presented by subject in a data listing. Subjects with protocol deviations will be listed individually, including subject number and observed deviation. Depending on the seriousness of the deviation, subject

👶 GALDERMA

might be excluded from the PP population, which shall be documented prior to database lock.

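### The visible SAP does not place per-protocol exclusion decisions ahead of the sponsor's pre-lock review of outputs, and its 10% trigger for the per-protocol analysis ignores treatment arm

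*SAP*

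**What the plan says.** **Review of outputs.** SAP 14.0 (Quality Control) states: "Galderma or its designee will review all tables, listings, and figures prior to final database lock". SAP 15.0 also mentions draft tables, in a sentence about the number of decimal places: that choice is made "after review of draft statistical tables and before database freeze". On listings, the same section says: "Data listings will provide all data either collected on the corresponding eCRF page or loaded directly into the database, unless otherwise indicated".

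**Source of the analyses.** Protocol 9.1 (Data management) states: "Statistical analyses will be generated in SAS using data from the locked datasets".

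**PP membership.** SAP 5.2 defines the set: "Includes all subjects in ITT who complete the Week 12 visit without any deviations considered to have substantial impact on the primary effectiveness outcome". SAP 7.0 adds that, depending on how serious a deviation is, a subject "might be excluded from the PP population, which shall be documented prior to database lock".

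**Role of PP.** SAP 5.3 makes ITT the main set: "The primary and secondary effectiveness analyses will be performed using the ITT analysis set". It repeats the primary and the first secondary analysis in PP only "if there is at least a 10% difference in the number of subjects between the PP and ITT sets".

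**The concern.** Completing Week 12 is a matter of fact, but whether a deviation had a substantial impact on the primary outcome is a matter of judgement. A PP repeat adds support to the ITT result only if those judgements were made without sight of outcomes by arm. SAP 14.0 and SAP 7.0 set the same kind of boundary, database lock, for the review of outputs and for the PP decisions. Neither says which comes first.

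The 10% trigger raises a second question. It counts exclusions over the whole trial. Exclusions concentrated in one arm are the case in which a PP comparison tells the reader most, and a pooled count can leave that comparison unrun.

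At stake is the credibility and availability of a supportive analysis. The primary analysis set is not affected.

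**Working it through.** **Part 1: order of events.** No arithmetic applies, so the passages are set side by side.

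- Review of all outputs: before final database lock (SAP 14.0).
- Judged PP exclusions documented: before database lock (SAP 7.0).
- Statistical analyses: from locked datasets (Protocol 9.1).

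A review in one week and PP decisions in the next, both before lock, would comply with every line above. The visible text does not exclude that sequence.

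Would such a review show the arms? SAP 6.0, 8.1 and 13.1 lay out disposition, baseline listings and adverse events by treatment. The efficacy table layout is not visible. The visible text does not say whether pre-lock drafts carry real or dummy codes. SAP 3.2 names only the evaluator as blinded. Sight of outcomes by arm is therefore possible under the visible text, but not shown to be planned.

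**Part 2: the 10% trigger.** The plan gives a rule and no derived count, so there is no figure to reproduce.

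Inputs: N = 140 (Protocol 4.2, approximate) and a threshold of 10% (SAP 5.3). The allocation ratio is not visible, so 1:1 (70 and 70) and 3:1 (105 and 35) are assumed. Let k be the number of ITT subjects not in PP, whether for non-completion or for deviations.

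1. Base = ITT: k/140 ≥ 0.10 gives k ≥ 14. PP runs from 14 exclusions.
2. Base = PP: k/(140 − k) ≥ 0.10 gives k ≥ 14/1.1 = 12.73. PP runs from 13 exclusions.
3. The two bases differ only at k = 13: 13/140 = 9.3% (not run) against 13/127 = 10.2% (run).
4. At k = 12, PP is unrun on either base: 12/140 = 8.6% and 12/128 = 9.4%.
5. If all 12 were in one arm, that arm would lose:

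| Assumed allocation | Arm size | Share excluded |
|---|---|---|
| 1:1 | 70 | 12/70 = 17.1% |
| 3:1 | 105 | 12/105 = 11.4% |
| 3:1 | 35 | 12/35 = 34.3% |

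6. A 10% condition applied within each arm on the ITT base would be met in all three rows.

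**Illustration of what selective exclusion could do.** Assume 60% to 80% response and five non-responders excluded from one arm.

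- Arm of 70: 42/65 = 64.6% (+4.6 points) to 56/65 = 86.2% (+6.2).
- Arm of 35: 21/30 = 70.0% (+10.0) to 28/30 = 93.3% (+13.3).

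These figures show direction and scale only. Five exclusions are 5/140 = 3.6% of ITT, so under the present rule PP would not be run unless at least eight more subjects (PP base) or nine more (ITT base) were also excluded.

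**The case against.** The strongest reply is that nothing here conflicts. A dry run on draft data before lock, followed by final outputs from locked data, satisfies both SAP 14.0 and Protocol 9.1. The SAP 15.0 sentence on draft tables concerns decimal places, which points towards a format check. These points stand, and they rule out reading the two documents as contradictory. They do not settle the order of PP decisions and review, because SAP 14.0 covers all outputs and is not limited to format.

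It can also be said that the safeguard may lie elsewhere. Protocol 4.4, most of Protocol section 10, SAP 10.1 and much of SAP 11.1 are withheld. Protocol 12.1 refers deviation handling to the monitoring manual, and SAP 14.0 refers to standard operating procedures. The SAP is also based on protocol version 3.0, whereas the visible protocol is version 5.0. This stands as a limit on the finding: the gap is in the visible text only.

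SAP 7.0 does already require exclusions to be documented before lock. That is a real control, but it does not put them before the review.

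On the trigger, ITT is the natural base because PP is a subset of it, and all exclusions falling in one arm is an extreme case. Both points are fair. The missing base is minor. The one-arm case shows what the rule permits, and no visible text suggests that it is likely.

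**Conclusion.** Two modest points hold. First, the visible SAP does not require PP membership to be fixed before outputs by arm are reviewed, and it does not say that those outputs are masked. Second, the pooled 10% condition can leave PP unrun when one arm has lost a substantial share: 12 exclusions, 8.6% of ITT, could be 11.4% to 34.3% of an arm under the allocations assumed here.

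A reader might infer more than this, in three ways that the documents do not support:

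- That SAP 14.0 contradicts Protocol 9.1. It does not, since a dry run before lock and final outputs after lock meet both.
- That the response shifts shown above bound the possible bias. They do not: they rest on assumed response rates, arm sizes and counts, they change with each, and five exclusions alone would not cause PP to be run.
- That the unstated base matters in itself. With 140 subjects it changes the outcome only at exactly 13 exclusions.

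Priority is minor, because the primary and secondary analyses use ITT and only the supportive PP analysis is exposed. Confidence is medium, given the withheld text.

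**What to change.** 1. **SAP 7.0:** finalise and sign the PP exclusion list, with a reason for each subject, before any output showing outcomes by actual treatment is produced. PP turns on the Week 12 visit and the primary outcome, while participation lasts about 17.5 months (Protocol 4.3), so this need not wait for final lock.
2. **SAP 14.0:** state that the pre-lock review uses dummy or masked treatment codes and contains no efficacy results by arm. Exposure displays and the related adverse event table can reveal the arm even under masked codes (SAP 12.0 and 13.1), so item 1 is the main protection.
3. **SAP 5.3:** run PP for the primary and first secondary analyses regardless of the 10% condition, and show exclusions by arm and reason. If the condition is kept, define it as a share of ITT within either arm.

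If withheld text or a procedure already fixes the order and the masking, a cross-reference in SAP 7.0 and 14.0 is enough for items 1 and 2. The cost is SAP wording, minor programming, an earlier sign-off and one extra supportive table set. Data collection and the primary ITT analysis do not change.
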